1 PROTOCOL SUMMARY

1.1 Synopsis

Title: A Randomized Controlled Trial of Topical Cannabidiol for the Treatment of Thumb Basal Joint Arthritis.

Study Description: To investigate the therapeutic potential of cannabidiol (CBD) as a topical treatment for thumb basal joint arthritis. **Rationale:** CBD is commonly being used as an over-the-counter treatment for arthritis-related pain, however no clinical trial has been performed to establish efficacy. **Hypothesis:** CBD is more effective than placebo for relieving pain and improving patient-reported outcomes for thumb basal joint arthritis.

Study Design: The study design will be a double-blind, randomized controlled trial with crossover. Treatment will be blinded to the subjects and investigators. Patients will be randomly assigned 2 weeks of the CBD or control and then crossover to the other condition for 2 additional weeks. Patients will apply a novel cream containing CBD at the thumb base joint twice daily for 1 hour. Subjects will be advised to observe for physiologic changes, skin changes, or other adverse effects.

Objectives & Endpoints:	Objectives	Endpoints
	Primary	
	To determine the therapeutic potential of CBD as a topical treatment for thumb basal joint arthritis.	
Hand Functional Assessment: Change from baseline hand functional assessment including grip, appositional, and oppositional pinch strength (kg); Kapandji score; and metacarpal phalangeal (MP) and interphalangeal (IP) range of motion.
 
Patient Reported Outcome Measures: Change from baseline in the PROMIS-29 (Patient-Reported Outcomes Measurement Information System) and PROMIS upper extremity tests. The PROMIS-29 is a free publicly available generic health related quality of life (HRQoL) measure consisting of indices of pain, pain interference, depression, anxiety, global function, and social interactions. The PROMIS upper extremity test utilizes item-response theory and Computer Adaptive Test to efficiently and precisely report patient symptoms and perceived function.

	Secondary	

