2.2 Background

Numerous studies have shown the safety and efficacy of topical CBD for the treatment of osteoarthritis in dogs (2) and rats (3). Topical administration has been shown to have increased regional bioavailability and attenuates inflammation and pain without significant side-effects. The dose of maximum absorption and efficacy seen in rats was shown to be 6.2 mg/day (3). To date, no studies have been performed to evaluate the safety and efficacy of topical CBD for the treatment of basal thumb arthritis in human subjects.

Nitecka-Buchta et al. performed a double-blind randomized controlled trial of topical CBD for 60 total patients with myofascial pain. Topical application of 67 mg CBD – including other minor cannabinoids – was applied to masseter muscles twice daily for 14 days in the case group. Visual Analog Scores (VAS) were reduced from 5.6 on Day 0 to 1.7 on Day 14 (70.2% reduction) in the case group, versus 5.1 on Day 0 and 4.6 on Day 14 (9.8% reduction) in the control group ($p = 0.00$). (4)

Xu et al. performed a randomized controlled trial with cross-over for topical CBD treatment of 29 patients with symptomatic lower extremity neuropathy. Topical application of 250 mg of pure CBD (case arm) was applied up to four (4) times daily for four (4) weeks, and then patients switched to emu oil (control arm) with the same application for 4 weeks followed by cross-over. They showed a statistically significant reduction in Neuropathic Pain Scale scores for intense (5.11 to 4.02) ($p=0.009$) and sharp (4.01 to 3.09) ($p<0.001$) pain between case and control arms. (5)

No side effects or adverse events were noted in either clinical trial.

We have designed a randomized, controlled crossover design clinical trial to assess the safety and efficacy of topical CBD versus placebo for the treatment of thumb basal joint arthritis.

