5 STUDY DESIGN

5.1 Overall Design

The study design will be a double-blind randomized controlled trial with crossover. Treatment will be blinded to the subjects and investigators. Patients will be randomly

assigned two (2) weeks of the case or control topical cream and then crossover to the other cream for two (2) more weeks. Patients will apply the cream at their thumb basal joint twice daily for one (1) hour. The subjects will be advised to observe for physiologic changes, skin changes, or other adverse effects. If mild to severe drug-related adverse events are noticed, the creams will be removed immediately and appropriate care and observation will be taken. Each condition will last for two (2) weeks and then subjects will be contacted by the study coordinator to facilitate crossover into the other condition. This study will last one year from the beginning of subject recruitment to data analysis. Subjects will be enrolled in this study for approximately six (6) weeks from Screening until the final Study Visit.

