8.2 Participant Discontinuation/Withdrawal

Participants are free to withdraw from participation in the study at any time upon request.

A participant's study treatment would be discontinued for the following reasons:

- Significant study intervention non-compliance
- If any clinical adverse event (AE), laboratory abnormality, or other medical condition or situation occurs such that continued participation in the study would not be in the best interest of the participant
- Disease progression which requires discontinuation of the study intervention
- If the participant meets an exclusion criterion (either newly developed or not previously recognized) that precludes further study participation
- Participant decision to withdraw from study treatment and/or the study.

The reason for participant discontinuation or withdrawal from study treatment will be recorded. Participants who sign the informed consent form and are randomized but do not receive the study intervention may be replaced. Participants who sign the informed consent form, and are randomized and receive the study intervention, and subsequently withdraw, or are withdrawn or discontinued from the study, will not be replaced.

Participants that withdraw from the study (not only from study treatment, but all study follow-up) will not be contacted for any further study visits.

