11 STATISTICAL CONSIDERATIONS

11.1 Statistical Hypotheses

Outcomes between the two groups will be compared and in a within-subject analysis will be performed given the crossover design. A descriptive analysis of the variables will be performed by calculating mean and standard deviation (SD), as appropriate, and absolute and percentage frequency. Differences between pre- and post-treatment scores (delta scores) will be assessed with the Wilcoxon signed-rank test. Correlations between delta scores and the variables considered [age, gender, body mass index (BMI), radiographic features] will be evaluated with the Spearman, Mann-Whitney, and Kruskal-Wallis tests. The significance threshold will be set at 0.05.

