11.2 Sample Size Determination

Based on a 95% confidence interval to show a 50% reduction effect (as shown in the literature) and receive 80% power with a population variance of 0.25, sample size analysis resulted in a sample size of at least 16. The UVA Hand Center performed 421 operative procedures in 2018 for the management of thumb basal joint arthritis among our 6 fellowship trained hand surgeons, and consequently has a volume sufficient to accrue 40 patients during the study period.

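### Section 11.1 gives no test, contrast or period term for CBD versus control; the one outcome test it names is before versus after treatment, which an inert cream can pass.

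*Combined protocol and SAP*

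**What the plan says.** The hypothesis in section 1.1 is comparative: "CBD is more effective than placebo for relieving pain and improving patient-reported outcomes for thumb basal joint arthritis". The primary endpoints are changes from baseline, for example "Change from baseline in the PROMIS-29", and the schedule in section 14.1 labels Day 0 as a baseline visit.

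The efficacy analysis is one paragraph, section 11.1. It opens with an intention: "Outcomes between the two groups will be compared and in a within-subject analysis will be performed given the crossover design". It then names one test for outcomes: "Differences between pre- and post-treatment scores (delta scores) will be assessed with the Wilcoxon signed-rank test". Spearman, Mann-Whitney and Kruskal-Wallis tests follow, but they relate the change scores to age, gender, BMI and radiographic features, not to treatment. The threshold is 0.05, with sidedness not stated.

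On the crossover itself, section 5.1 says that after two weeks "subjects will be contacted by the study coordinator to facilitate crossover into the other condition". No washout is described, and no period, sequence or carryover term appears anywhere. Section 8.2 adds that treated subjects who "subsequently withdraw, or are withdrawn or discontinued from the study, will not be replaced".

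**The concern.** A signed-rank test on scores before and after treatment asks whether subjects changed. It does not ask whether they changed more on CBD than on control. Placebo response, regression to the mean, or practice on the grip and pinch tests can all produce a significant change on an inert cream.

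The text supports two readings.

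- **Reading (a), literal.** Scores are tested before against after, cream by cream. CBD is never tested against control.
- **Reading (b), charitable.** Each subject's change on CBD is paired with that subject's change on control, and the signed-rank test is applied to the difference. Shared placebo response then cancels, but the analysis takes no account of period.

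The two readings have very different error rates. Section 11.1 does not choose between them, does not say which visits count as before and after, and does not confirm that Day 0 is the reference for the second period. The method could therefore be chosen after the data are seen. Section 8.1 also lists meeting the primary endpoint as a ground for stopping the study, and no stated test defines when that has happened.

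**Working it through.** **1. The plan's sample size.** Inputs from section 11.2: effect 0.5 (the 50% reduction), variance 0.25, 80% power. A two-sided 0.05 level is assumed, and effect and variance are taken to share one scale. (1.96 + 0.842)² = 7.85.

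| Design | Formula | n |
|---|---|---|
| Two arms | 2 × 7.85 × 0.25 / 0.5² = 15.7 | 16 per arm |
| 2×2 crossover, within-subject variance 0.25 | 7.85 × (2 × 0.25) / 0.5² = 15.7 | 16 in total |
| One-group before/after, SD of change 0.5 | 7.85 × 0.25 / 0.5² = 7.85 | 8 (10 with the t distribution) |

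The stated minimum of 16 fits a CBD-versus-control comparison, not a before/after test.

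**2. Reading (a): an inert cream.** Section 2.2 reports a control-group VAS of "5.1 on Day 0 and 4.6 on Day 14 (9.8% reduction) in the control group", a fall of 0.5 points. The documents give no SD of change. Two scalings are used: 9.8% against the SD implied by "80% power with a population variance of 0.25" (√0.25 = 0.5), and 0.5 points against assumed SDs. The chance of a significant improvement is roughly Φ(d√(3n/π) − 1.96), where d is the mean change divided by its SD. For d = 0.196 and n = 40 this is Φ(1.21 − 1.96) = 23%. Simulation with normal data gives:

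| Mean change / SD | d | False improvement, n = 40 |
|---|---|---|
| 0.098 / 0.5 | 0.196 | 22% |
| 0.5 / 2.5 | 0.20 | 23% |
| 0.5 / 2.0 | 0.25 | 33% |
| 0.5 / 1.5 | 0.33 | 53% |
| 0.5 / 1.0 | 0.50 | 85% |

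At the stated minimum of 16 subjects the range is 10% to 45%. The nominal rate in this direction is 2.5%. On the same data the direct CBD-minus-control test gives 2.2% to 2.8%. With both creams inert and a shared Day 0 baseline, CBD is significant and control is not in about 9% to 17% of trials.

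**3. Reading (b): no period term.** Let T be the CBD effect and p the period 1 minus period 2 shift. The CBD-minus-control difference has mean T + p when CBD comes first and T − p when control comes first. With equal sequences p averages out but inflates the estimated variance. With n₁ and n₂ completers the bias is p(n₁ − n₂)/(n₁ + n₂); for 12 versus 20 and p = 0.5 its size is 0.5 × 8/32 = 0.125.

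Simulation with assumed error SD 0.7 and T = 0.5, 20 per sequence:

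| Period shift | Power, no period term | Power, rank-sum between sequences |
|---|---|---|
| 0 | 86% | 85% |
| 0.35 | 83% | about 86% |
| 0.5 | 79% | about 86% |
| 0.7 | 72% | about 86% |

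For T = 0 and a shift of 0.5 to 0.7, type I error without a period term is 7% to 8% with 12 versus 20 completers, near 5% with 14 versus 20, and 2% to 3% with 18 versus 20.

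**4. The proposed contrast.** (Day 14 − Day 0) − (Day 28 − Day 0) = Day 14 − Day 28, so Day 0 cancels. The mean is T + p for CBD first and −T + p for control first. The sequences differ by 2T, half of that is T, and p drops out.

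**5. Carryover (hypothetical).** If a fraction f of the CBD effect remains at Day 28 in subjects who had CBD first, their mean becomes T(1 − f) + p and the estimate becomes T(1 − f/2). For f = 0.25 or 0.5 it falls by 12.5% or 25%, and power falls from about 85% to 75% or 62%.

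**The case against.** The strongest defence is that section 11.1 does commit to comparing the groups and to a within-subject analysis, in the sentence just before the signed-rank test. The sample size supports this, since 16 reproduces for a treatment contrast and not for a before/after test. On that view the authors meant reading (b) and the fault is incomplete drafting. This shows what was probably intended. It does not supply the missing test, and the one test that is written down is defined on scores before and after treatment.

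The size of the problem under reading (a) can also be challenged. The 0.5-point fall comes from a trial in masseter myofascial pain, VAS is not a listed endpoint here, and the SDs of change are assumed. The 22% figure further assumes that the 9.8% and the variance of 0.25 share a scale. That assumption is consistent with the reading of section 11.2 that reproduces 16, but it is not stated there. The rates are illustrations, not predictions. The n = 16 figures describe the stated minimum, not the planned 40.

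The period term is rightly called the smaller part. With light, even attrition its omission is conservative, and inflation needs eight more losses in one sequence than in the other. Carryover is a separate matter that the fix does not cure.

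Finally, a mixed model could serve as the primary analysis instead of a rank test. Either would do. The rank test is preferred here because it stays closest to the plan, but it drops subjects with only one period, so the model is needed alongside it.

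**Conclusion.** The concern holds and must be fixed. Followed as written, section 11.1 does not test the trial's hypothesis, and no other section repairs it.

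Under the literal reading, an inert cream would appear to work in roughly 22% to 85% of trials of 40 subjects, against a nominal 2.5%. That range rests on the cited control response carrying over to this setting and on the SDs shown. Any non-zero shared improvement pushes the rate above nominal.

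Under the charitable reading that risk disappears. What remains is a loss of about 3 to 14 power points for the period shifts considered, and type I error of 7% to 8% only if completion is very unequal. Confidence in the main point is high, because it rests on the text rather than on the simulations.

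**What to change.** Rewrite section 11.1 to name one primary method for CBD versus control.

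- **Contrast and test.** For each subject take Day 14 minus Day 28, the ends of the two treatment periods. Compare the two sequences with a two-sided Wilcoxon rank-sum test at 0.05. Report half the Hodges-Lehmann shift, with its 95% confidence interval likewise halved, as the CBD-minus-control effect.
- **Baseline.** State that change from baseline uses Day 0 in both periods.
- **Sensitivity analysis.** Fit a mixed model with treatment, period and sequence as fixed effects and subject as random, keeping subjects who have only one period.
- **Carryover.** State that, with no washout, carryover of the CBD effect would bias the contrast towards no difference. A period-1-only comparison may be reported, labelled as low power: 32% (rank-sum on change) to 39% (baseline-adjusted) under the same assumptions with a between-subject SD of 1.
- **Before/after tests.** Keep them as descriptive only.

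The visit must be named because sections 9.1 and 14.1 also schedule outcomes on Days 7 and 21. This change does not settle which of the several listed outcomes is primary; that choice has to be stated as well.

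The cost is rewording section 11.1. All the visits used are already scheduled, and no extra patients or data are needed.

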4 OBJECTIVES AND ENDPOINTS

Objectives	Endpoints
Primary	
To determine therapeutic potential of CDB as a topical	Hand Functional Assessment: Change from baseline in hand functional assessment including grip, appositional,

treatment for thumb basal joint arthritis.	
and oppositional pinch strength (kg); Kapandji score; and MP and IP range of motion.
 
Patient Reported Outcome Measures: Change from baseline in the PROMIS-29 (Patient-Reported Outcomes Measurement Information System) and PROMIS upper extremity tests. The PROMIS-29 is a free publicly available generic health related quality of life (HRQoL) measure consisting of indices of pain, pain interference, depression, anxiety, global function, and social interactions. The PROMIS upper extremity test utilizes item-response theory and Computer Adaptive Test to efficiently and precisely report patient symptoms and perceived function.

Secondary	
To determine the safety of treatment CBD.
 
Safety will be determined by evaluating:
 
 • The frequency and severity of adverse events from the beginning of treatment through the end of study participation. • Changes in skin appearance from baseline using standardized skin assessment tool (patient will be removed from study with a score ≥ 2) • Clinically significant change in CBC (baseline and weekly follow-up) • Clinically significant change in basic metabolic panel (i.e., BUN, creatinine, CO₂, Cl, K, Na, and glucose) (baseline and weekly follow-up) • Clinically significant change in hepatic function testing (i.e., serum transaminases [ALT/AST], total bilirubin, and alkaline phosphatase) (baseline and weekly follow-up) • Clinically significant change in vital sign assessments (i.e., heart rate and blood pressure) • Suicidal behavior and thoughts as a specific question using the Columbia-Suicide Severity Rating Scale (C-SSRS) at baseline and follow-up.

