5.3 End of Study Definition

Primary completion date is the date that the final participant was examined or received an intervention for the purposes of final collection of data for the primary outcome, whether the clinical study concluded according to the pre-specified protocol or was terminated. In the case of clinical studies with more than one primary outcome measure with different completion dates, this term refers to the date on which data collection is completed for all of the primary outcomes defined as the final date for the collection of data for the primary endpoint.

Study completion date is the date the final participant was examined or received an intervention for purposes of final collection of data for the primary and secondary outcome measures and adverse events (for example, last participant's last visit), whether the clinical study concluded according to the pre-specified protocol or was terminated.

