9 STUDY ASSESSMENTS AND PROCEDURES

9.1 Clinical Assessments

Hand Functional Assessment: Hand functional assessment will include grip, appositional, and oppositional pinch strength (kg); Kapandji score; and MP and IP range of motion. Assessments will be performed at Baseline and study Days 7, 14, 21, and 28.

Patient Reported Outcome Measures: The PROMIS-29 and PROMIS upper extremity tests will be collected. The PROMIS-29 is a free publicly available generic HRQoL measure consisting of indices of pain, pain interference, depression, anxiety, global function, and social interactions (Attachment 1, Appendix 14.4) Subjects will complete the measure at Baseline and study Days 7, 14, 21, and 28. The PROMIS upper extremity test utilizes item-response theory and Computer Adaptive Test to efficiently and precisely report patient symptoms and perceived function. Subjects will complete the measure in clinic using an iPad. The PROMIS upper extremity assessment is provided in Attachment 2 (Appendix 14.4). Subjects will complete the PROMIS assessment at Baseline and study Days 7, 14, 21, and 28.

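### Eight to thirteen primary outcomes share one unadjusted 0.05, with no success rule, primary visit or fixed contrast, so the error rate of a positive claim is not controlled

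*Combined protocol and SAP*

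**What the plan says.** The Synopsis (1.1) and Section 4 place two groups of endpoints under a single primary objective. The first is "Change from baseline hand functional assessment including grip, appositional, and oppositional pinch strength (kg); Kapandji score", together with MP and IP range of motion, which makes six measures. The second is change in the PROMIS-29 and in the PROMIS upper extremity test. The PROMIS-29 is described as "consisting of indices of pain, pain interference, depression, anxiety, global function, and social interactions", which names six indices, and no summary score is defined.

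Section 9.1 sets the timing of hand function: "Assessments will be performed at Baseline and study Days 7, 14, 21, and 28". The PROMIS measures follow the same days. Each two-week condition therefore has two post-baseline visits, and neither is named as primary.

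Section 11.1 promises both a comparison between groups and a within-subject analysis. The test it describes is this: "Differences between pre- and post-treatment scores (delta scores) will be assessed with the Wilcoxon signed-rank test". It then adds "The significance threshold will be set at 0.05".

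The hypothesis in the Synopsis is narrower than the endpoint list: "CBD is more effective than placebo for relieving pain and improving patient-reported outcomes for thumb basal joint arthritis". Hand function is not mentioned there.

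**The concern.** A reader cannot tell from the plan which result would make the trial positive. If every primary outcome had to succeed, testing each at 0.05 would cause no inflation. If one significant outcome is enough, 0.05 is not the error rate of that claim. A chance finding on one measure at one visit could then be reported as the primary result while the rest are null. The plan states neither rule, so the choice could be made after the data are seen.

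The contrast is also open. A literal pre-versus-post test can be significant because of change unrelated to CBD. The question of interest is CBD against control.

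Other sections do not settle the matter. Section 11.2 names no outcome for the sample size. Section 5.3 refers to "all of the primary outcomes defined as the final date for the collection of data for the primary endpoint", mixing plural and singular without identifying either. Section 8.1 lists demonstrated efficacy and a met primary endpoint as termination grounds, although no single primary endpoint exists and no interim analysis is planned. Those passages need reconciling, but no inflation from them is scheduled and none is counted below.

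**Working it through.** **Count.** 6 hand-function measures + PROMIS-29 + PROMIS upper extremity = 8. With the six named PROMIS-29 indices counted separately, 6 + 6 + 1 = 13.

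**The plan's own figure.** Section 11.2 says the trial would "receive 80% power with a population variance of 0.25, sample size analysis resulted in a sample size of at least 16". Reading the 50% reduction as a difference of 0.5, with two-sided 0.05:

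n = 2 × 0.25 × (1.960 + 0.842)² / 0.5² = 15.7, rounded up to 16.

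This fits 16 per arm in parallel groups. It also fits 16 pairs if the two measurements are uncorrelated. Either way it is one test of one unnamed outcome at 0.05, with no allowance for multiplicity.

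**False-positive risk.** Assumptions: CBD has no effect, there is one CBD-versus-control test per outcome at one visit, any one p<0.05 is claimed, and all pairs of outcomes have equal correlation r. The plan does not state sidedness; two-sided is assumed. With m outcomes and c = 1.96:

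- For r = 0: risk = 1 − 0.95^m. For m = 13 this is 1 − 0.513 = 48.7%. For m = 8 it is 1 − 0.663 = 33.7%.
- For r > 0: risk = 1 − ∫ φ(u) [Φ((c − √r·u)/√(1−r)) − Φ((−c − √r·u)/√(1−r))]^m du.
- Counting only results that favour CBD (nominal 2.5%), the lower limit is dropped. At r = 0 this is 1 − 0.975^m.

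| | r = 0 | 0.5 | 0.7 | 0.9 |
|---|---|---|---|---|
| 13 outcomes, either direction | 48.7% | 33.4% | 24.1% | 13.8% |
| 8 outcomes, either direction | 33.7% | 25.0% | 19.1% | 11.9% |
| 13 outcomes, favouring CBD | 28.0% | 16.7% | 12.0% | 6.9% |
| 8 outcomes, favouring CBD | 18.3% | 12.5% | 9.5% | 6.0% |

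**Checks.**

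- *Unequal correlation.* With assumed correlation 0.5-0.7 within hand function and within PROMIS, and 0.2 between them, the two-sided risk is 31-38% for 13 outcomes and 23-27% for 8 (400,000 draws).
- *The planned test.* Exact signed-rank tests simulated at 40 pairs (20,000 runs) give, at r = 0 / 0.5 / 0.7 / 0.9, 48.3 / 34.3 / 25.9 / 14.8% for 13 outcomes and 33.4 / 25.0 / 20.0 / 12.7% for 8. These agree with the table to within 2 points.
- *Sidedness.* With one-sided tests at 0.05, the ranges for r from 0.7 to 0 are 20.6-48.7% (13) and 16.8-33.7% (8).
- *Holm.* In the same simulation with 13 outcomes, Holm brings the risk to 1.7-4.7%.

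**Power cost of Holm at its strictest step (0.05/13).** Inputs are a difference of 0.5 and variance 0.25, so the SD of the within-subject difference is √(2 × 0.25 × (1 − ρ)). The within-subject correlation ρ is not in the plan and is assumed. The 32 pairs reflect an assumed 20% loss from 40; Section 8.2 does not replace treated subjects who withdraw. Ranges run from the normal approximation to the exact test.

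| Pairs | ρ | Power at 0.05 | Power at 0.05/13 |
|---|---|---|---|
| 40 | 0 | 0.989 | 0.882-0.894 |
| 40 | 0.3 | 0.999 | 0.976-0.980 |
| 40 | 0.5 | 1.000 | 0.998-0.999 |
| 32 | 0 | 0.966 | 0.742-0.773 |
| 32 | 0.3 | 0.995 | 0.914-0.929 |
| 32 | 0.5 | 1.000 | 0.984-0.988 |

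**The case against.** The gap itself is not in dispute. The strongest objections concern its size and scope.

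- **Direction.** The hypothesis favours CBD, so a chance result favouring control would not be claimed as success. This is fair. The absolute risk of a false CBD claim is about half the two-sided figure, though the inflation relative to 2.5% is similar.
- **Independence.** The 34% and 49% figures need uncorrelated outcomes, which is unlikely for related measures in one patient. They stand as upper bounds. Even at correlation 0.9 with 8 outcomes, the two-sided risk is more than double 0.05.
- **Count.** The endpoint is worded as the PROMIS-29, and its indices appear in a description of the instrument. That supports 8 as the literal count. Both counts lead to the same conclusion.
- **Scope of the hypothesis.** If only patient-reported outcomes governed the claim, there would be 2 instruments, or 7 outcomes with the indices separate. The risk favouring CBD would then be about 3.5-5% or 6-16%, at correlations from 0.9 to 0. The plan nonetheless lists hand function as primary.
- **Visit.** Days 14 and 28 are the natural post-treatment points. The plan does not say so.
- **Period-2 baseline.** The Schedule of Activities shows no separate one. With a single Day 0 baseline, that baseline cancels: (CBD end − Day 0) − (control end − Day 0) = CBD end − control end.
- **Sample-size inputs.** The 0.5 and 0.25 belong to an unnamed outcome without units, so the power figures are only indicative for any particular measure.

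**Conclusion.** The concern holds and should be fixed before unblinding. The documents establish that the error rate of a positive claim is uncontrolled; they do not establish one particular size for it. The figures rest on the any-one-success rule, assumed correlations, a single visit, and the CBD-minus-control contrast. Free choice among visits would raise them, and an all-must-succeed rule would remove the inflation. They do not apply to the pre-versus-post test as Section 11.1 literally words it. For that test, significance would not by itself be evidence of a CBD effect.

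**What to change.** Revise Sections 1.1, 4 and 11.1 in one of two ways.

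**A. One primary outcome.** The investigators choose it from the stated hypothesis: pain or another patient-reported outcome, for example one of the two pain-related PROMIS-29 indices. It is tested at end of period (Day 14 / Day 28) at two-sided 0.05. The other measures and Days 7 and 21 become secondary with Holm adjustment, or exploratory with confidence intervals. The cost is that some measures lose primary status.

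**B. Keep the set.** Fix end of period as the primary visit, state whether the PROMIS-29 is one outcome or six, and apply Holm across the set. The cost is power. With 13 outcomes at the strictest step and ρ = 0 / 0.3 / 0.5, the loss is about 9-11 / 2 / under 1 points at 40 complete pairs, and about 19-22 / 7-8 / 1-2 points at 32. Later Holm steps, or a set of 8, cost less.

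In either case, Section 11.1 should state that the signed-rank test is applied to the within-subject CBD-minus-control difference. Sections 5.3 and 8.1 should be reconciled with whatever is named primary. All of this is protocol and SAP wording and needs no new data.
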